9.2.5. Respiratory Parameters: Spirometry

Spirometry (FEV₁, FVC, FEV₁/FVC) will be performed at several timepoints as specified in the [Time and Events Schedule](#). Spirometry may also be investigated at any time following respiratory signs or symptoms (repeated coughing, bradypnea, tachypnea, rales and rhonchi) of respiratory difficulties. Spirometry will be performed as per hVIVO's Operating Instruction. In case of respiratory difficulties, the investigator may decide to perform additional lung function testing.

Spirometry will be done for each subject at approximately the same timepoint on each day from Day 0.

At each timepoint, three technically acceptable measurements will be recorded using a spirometer. The best reading from each assessment (as provided by the spirometry machine) will be used for analysis.

The following data will be automatically calculated:

- FEV₁ % predicted;
- FEV₁/FVC ratio (absolute, not predicted);

Any clinically relevant changes in pulmonary function occurring during the study will be recorded on the Adverse Event Section of the eCRF.

9.2.6. Safety Evaluations

Any clinically relevant changes occurring from ICF signature until discharge from the Unit must be recorded on the eCRF. Any clinically significant abnormalities, including those persisting at the end of the study/early withdrawal, will be followed by the investigator until resolution or until a clinically stable endpoint is reached.

Adverse events occurring from ICF signature until 28 days after vaccination will be examined for relationship to study vaccine. Adverse events occurring from admission to the quarantine Unit until 28 days after challenge will be evaluated for relationship to the challenge.

The study will include the evaluations of safety and tolerability outlined in the following sections according to the timepoints provided in the [Time and Events Schedule](#).

9.2.6.1. Adverse Events

Unsolicited AEs will be reported by the subject from ICF signature until 28 days after vaccination, and from the entry into the Unit until 28 days after challenge. Solicited AEs will be reported by the subject for 7 days after vaccination via the subject diary. Adverse events will be followed by the investigator as specified in Section [12.3](#).

For solicited AEs, the following applies:

- **Solicited Adverse Events**

Information related to solicited events as defined in Section [12.1.1](#), will be recorded by subjects in a diary for 7 days after vaccination. Each subject will be provided with a diary and instructions on how to complete the diary (Section [9.1.1](#)). There will be a minimum 30-minute post-vaccination assessment of solicited events at the site. Diary information will be transcribed by the study personnel in the appropriate eCRF pages.

Subjects will be asked to note in the diary occurrences of pain/tenderness, erythema and induration/swelling at the study vaccine injection site daily for 7 days post-vaccination. The extent (largest diameter) of any erythema, and induration/swelling should be measured (using the ruler supplied) and recorded daily. Induration/swelling should also be graded using the functional scale.

- **Injection Site Pain/Tenderness**

Injection site pain (eg, stinging, burning) is an unpleasant sensory and emotional experience associated with actual or potential tissue damage and occurring at the immunization site (with or without involvement of surrounding tissue). Injection site tenderness is a painful sensation localized at the injection site upon palpation and/or movement of the limb. Due to subjective nature of the reaction, the severity assessment of pain/tenderness is self-reported (if a subject is unable to provide self-report, other reporters include family member/caregiver or health care provider).¹²

- **Injection Site Erythema**

Injection site erythema is a redness of the skin caused by dilatation and congestion of the capillaries localized at the injection site. It can best be described by looking and measuring.

- **Injection Site Swelling/Induration**

Injection site swelling is a visible enlargement of an injected limb. It may be either soft (typically) or firm (less typical). Injection site induration is a palpable thickening, firmness, or hardening of soft tissue, usually has well-demarcated palpable borders, can be visible (raised or sunken compared to surrounding skin), is often 'woody' to touch and has a flat shape. As differentiation between swelling and induration may be difficult without health care professional's assessment, both symptoms have been combined to allow self-assessment by the subjects. Both swelling and induration can best be described by looking and measuring.

Note: any other injection site events not meeting the above case definitions should be reported separately as unsolicited AEs.^{20,21}

Systemic Adverse Events

Subjects will be instructed on how to record daily temperature using a thermometer provided for home use. Subjects should record body temperatures in the diary in the evening of the day of vaccination, and then daily for the next 7 days approximately at the same time each day.^a If more than one measurement is made on any given day, the highest temperature of that day will be used in the eCRF.

^a The 7-day post-vaccination temperature measurements may be taken earlier to coincide with the corresponding clinic visit.

Fever is defined as endogenous elevation of body temperature $\geq 38^{\circ}\text{C}$, as recorded in at least one measurement.²⁴

Subjects will also be instructed on how to note daily in the diary for 7 days after vaccination symptoms of the following events: fatigue, headache, myalgia, arthralgia, chills, nausea, and fever (ie, body temperature $\geq 38^{\circ}\text{C}$).

The severity of these solicited systemic AEs will be graded by the investigator according to the criteria presented in Section 12.1.3.

If a solicited local or systemic AE is not resolved by 7 days after vaccination, the follow-up will be captured on the diary. The subject will be instructed to record the date of last symptoms and maximum severity in the diary after resolution.

9.2.6.2. Clinical Laboratory Tests

Blood and urine samples for laboratory safety assessments will be collected for screening up to 56 days prior to vaccination, pre-vaccination, 7 days post-vaccination, and prior to challenge on Day -1 or Day -2. Blood samples will additionally be collected at discharge from the quarantine Unit and at 28 days post-challenge. The following tests will be performed by a local laboratory (*parameters only measured at screening):

- **Hematology Panel**

- platelet count.
- white blood cell (WBC) count (absolute)
- WBC differential
 - neutrophils
 - lymphocyte
 - monocytes
 - eosinophils
 - basophils
- red blood cell (RBC) count
- reticulocyte count (% and absolute)
- hemoglobin
- hematocrit
- mean corpuscular volume (MCV)
- mean corpuscular hemoglobin (MCH)
- MCH concentration (MCHC)

- **Biochemistry Panel**

- sodium
- potassium
- glucose (random)
- albumin

chloride
bicarbonate
calcium
uric acid
total protein
creatinine
total, direct, and indirect bilirubin
inorganic phosphate
blood urea nitrogen
C-reactive protein
gamma glutamyl transferase
alkaline phosphatase
alanine transaminase
lactate dehydrogenase
aspartate transaminase
urea

- **Cardiac Enzymes** (done together with ECGs on admission, and on Days 3, 7 and 11)

Troponin T
creatinine kinase

- **Urinalysis** – dipstick for:

specific gravity
pH
glucose
protein
blood
ketones
appearance
color
nitrite
urobilinogen
bilirubin
leucocytes

A repeat urinalysis will be performed in the event of a positive dipstick test. Microscopic reflex testing will be carried out if the repeat urinalysis dipstick test is also positive.

Review and Grading of Laboratory Data

The investigator must review each laboratory result, document this review and assess systematically any clinical significance. The laboratory reports must be filed with the source documents.

Laboratory values will be initially evaluated by the investigator according to local laboratory criteria. Abnormal values outside the local laboratory range of normal will be graded according to the FDA Guidance document “Toxicity Grading Scale from Healthy Adult and Adolescent Volunteers Enrolled in Preventive Vaccine Clinical Trials” (see [Attachment 1](#)). Laboratory values within local laboratory normal limits will not be FDA graded and will be considered as normal.

Reporting Laboratory Abnormalities as AEs

Any clinically significant abnormal laboratory value within 28 days post-vaccination that falls outside of the local laboratory normal range and that requires follow-up will be captured as an AE. Laboratory values outside normal ranges that are not clinically significant in the judgment of the investigator, should not be recorded as AEs.

Any laboratory value falling within the local laboratory normal range will not be severity graded or recorded as an AE, regardless of whether the value falls within FDA ranges for Grade 1 or higher.

Note: Values for parameters falling within the local laboratory normal range should not be reported as AEs.

Repeat of Clinically Significant Laboratory Tests

For any clinically significant abnormal laboratory value that has increased in grade over baseline, the test must be repeated at the next scheduled visit or sooner based on the investigator’s judgment, however Grade 3 abnormalities should be retested within 48 hours. Any clinically significant abnormalities (including those persisting at the end of the study or at early withdrawal) will be followed by the investigator until resolution or until a clinically stable endpoint is reached (see Section [12.3](#)).

Screening Procedures

For entry into the study, each subject must be healthy on the basis of clinical laboratory tests performed within 56 days of vaccination. Enrollment of a subject with laboratory values outside of the local laboratory normal range representing FDA toxicity Grade 1 is allowed if the investigator considers the values reasonable for the population under study and not clinically significant.

Additional Clinical Laboratory Assessments

Additional clinical laboratory assessments to be performed are as follows:

- Serology testing (HIV type 1 or type 2, hepatitis B, hepatitis C) within 56 days of vaccination
- Serum pregnancy testing (β -hCG) for all female subjects within 56 days of vaccination and at entry to the quarantine Unit

- Urine pregnancy testing for all female subjects pre-vaccination
- Urine drug screen at screening and at entry to the quarantine Unit

9.2.6.3. Electrocardiogram

Supine 12-lead ECGs will be performed within 56 days of vaccination and on Day –1 or Day –2 prior to challenge; ECGs will only be performed at other times during the study if clinically indicated based on signs and symptoms. ECGs will be interpreted locally.

For 30 minutes prior to the ECG, subjects should refrain from meals, hot or cold beverages and strenuous exercise, and should remain in a room with a comfortable temperature. Each ECG should be obtained after the subject has been at rest for at least 5 minutes.

Enrollment of a subject with abnormal ECG results is allowed as long as the investigator feels that these are not clinically significant and appropriate for the population.

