4. SUBJECT POPULATION

The inclusion and exclusion criteria for enrolling subjects in this study are described in the following two subsections. If there is a question about the inclusion or exclusion criteria below, the investigator must consult with the appropriate sponsor representative and resolve any issues before enrolling a subject in the study. Waivers are not allowed.

Screening for eligible subjects will be performed between 56 days to 3 days before vaccination. Historical pre-screening data collected through the ethics committee-approved hVIVO screening protocol within 56 days (90 days for viral serology) to 3 days prior to vaccination may be used for screening procedures. Historical pre-screening data obtained prior to this window can be re-assessed any time from 40 days to 3 days prior to vaccination.

Each potential subject must satisfy all of the following criteria to be enrolled in the study.

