4.1. Inclusion Criteria

- 1 Each subject must sign an ICF indicating that he or she understands the purpose of and procedures required for the study, is willing to participate in the study and attend all scheduled visits, is willing to be isolated and stay in the clinic for the quarantine phase, and is willing and able to comply with all study procedures and adhere to the prohibitions and restrictions specified in this protocol.
- 2 Subject is a man or woman, ≥ 18 to ≤ 50 years old on the day of ICF signature.
- 3 Subjects must be in good health, without significant medical illness, on the basis of a medical evaluation that reveals the absence of any clinically relevant abnormality and includes a physical examination (including height and weight), skin examination, medical history, vital signs (systolic and diastolic blood pressure and heart rate, respiratory rate, and body temperature), and the results of clinical laboratory tests performed within 56 days of vaccination. If there are abnormalities, the subject may be included only if the investigator judges the abnormalities or deviations from normal to be not clinically significant. This determination must be recorded in the subject's source documents and initialed by the investigator.
- 4 Subjects must have a non-clinically significant 12-lead ECG within 56 days of vaccination including:

- a) normal sinus rhythm (heart rate between 50 and 100 beats per minute [bpm], extremes included)
- b) QT interval corrected for heart rate according to Fridericia (QTcF) interval ≤ 450 ms
- c) QT interval corrected for heart rate according to Bazett (QTcB) interval ≤ 450 ms
- d) QRS interval < 120 ms
- e) PR interval ≤ 210 ms.

Note: Retesting of abnormal ECG values that may lead to exclusion will be allowed once without prior approval from the sponsor. Repeat ECG due to equipment failure will not count as a retest. Subjects with a normal value at retest may be included.

- 5 Subjects must be sero-suitable for RSV within 90 days of vaccination (low immunity to the RSV-A Memphis 37b virus using a virus neutralization assay).

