- 6 Subject must be healthy on the basis of clinical laboratory tests performed within 56 days of vaccination. If the results of the laboratory screening tests are outside the local laboratory normal reference ranges and additionally within the limits of toxicity Grade 1 according to the US Food and Drug Administration (FDA) toxicity tables (ie, for tests in the FDA table^a), the subject may be included only if the investigator judges the abnormalities or deviations from normal to be not clinically significant and appropriate and reasonable for the population under study. This determination must be recorded in the subject's source documents and initialed by the investigator.

Note: If laboratory screening tests are out of local laboratory normal ranges and deemed clinically significant, repeat of screening tests is permitted once using an unscheduled visit during the screening period to assess eligibility.

- 7 Contraceptive use by men or women should be consistent with local regulations regarding the use of contraceptive methods for subject participating in clinical studies.

Before randomization, a woman must be either:

- a. Not of childbearing potential defined as:
 - i. Premenarchal: *a premenarchal state is one in which menarche has not yet occurred.*
 - ii. postmenopausal: *amenorrhea for at least 12 months without an alternative medical cause.*
 - iii. permanently sterile: *permanent sterilization methods include hysterectomy, bilateral salpingectomy, bilateral tubal occlusion/ligation procedures, and bilateral oophorectomy.*
- b. Of childbearing potential and

^a For the FDA toxicity grading tables, see [Attachment 1](#): FDA Guidance document "Toxicity Grading Scale for Healthy Adult and Adolescent Volunteers Enrolled in Preventive Vaccine Clinical Trials" (September 2007).

- i. practicing an acceptable effective method of contraception. Acceptable methods for this study include:
 - hormonal contraception;
 - intrauterine device;
 - intrauterine hormone-releasing system;
 - male or female condom with or without spermicide;
 - cap, diaphragm or sponge with a vaginal spermicide;
 - vasectomized partner (the vasectomized partner should be the sole partner for that subject);
 - sexual abstinence*.

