Subjects with laboratory values not meeting eligibility criteria at the screening visit may have one repeat testing at the discretion of the investigator if the abnormality is not clinically significant and may be a testing aberrancy. Enrollment of a subject with laboratory values representing toxicity Grade 1 is allowed if the investigator considers the values not to be clinically significant and reasonable for the population under study. Details on toxicity grade assessment are provided in Section 12.1.3.

After laboratory data, medical history, physical examination, ECG and nasopharyngeal swab/nasal wash tolerance data have been reviewed for completeness and adherence to inclusion and exclusion criteria, the subject can be deemed eligible for the study.

Unsolicited AEs will be recorded on the AE page of the eCRF from ICF signature until 28 days after vaccination, and from the entry into the Unit until 28 days after challenge. SAEs will be collected from ICF signature until 6 months after vaccination (ie, the end of the study).

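### The fixed screening ECG limits in inclusion criterion 4 conflict with the investigator discretion given in Protocol Section 9.2.6.3

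*Protocol*

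**What the plan says.** **ECG.** Criterion 4 in Protocol Section 4.1 opens with "Subjects must have a non-clinically significant 12-lead ECG within 56 days of vaccination including" and then lists five items: sinus rhythm with a heart rate of 50-100 bpm, QTcF at most 450 ms, QTcB at most 450 ms, QRS below 120 ms and PR at most 210 ms. Its note says "Retesting of abnormal ECG values that may lead to exclusion will be allowed once without prior approval from the sponsor", and that a volunteer whose value is normal at retest may be included. The introduction to Section 4 makes all inclusion criteria mandatory, sends questions about a criterion to the sponsor before enrolment, and states "Waivers are not allowed".

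Section 9.2.6.3 gives a different rule: "Enrollment of a subject with abnormal ECG results is allowed as long as the investigator feels that these are not clinically significant". The sentence goes on to require that the results suit the study population. It names no limits and does not mention criterion 4.

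**Laboratory repeats.** The note to criterion 6 says "If laboratory screening tests are out of local laboratory normal ranges and deemed clinically significant, repeat of screening tests is permitted once". Section 9.1.3 says that volunteers whose values miss the eligibility criteria "may have one repeat testing at the discretion of the investigator if the abnormality is not clinically significant and may be a testing aberrancy".

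**The concern.** Two sections decide the same question, whether a volunteer with an out-of-limit screening ECG may enter, and they answer it on different grounds. One uses numbers and a retest. The other uses the investigator's judgment. Staff applying different sections could reach opposite decisions on the same tracing, each with text to support them.

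This matters because the criteria are the entry screen for healthy volunteers who receive an investigational vaccine and then a live virus. Section 1.3.5 counts strict application of the inclusion and exclusion criteria among the measures that make the benefit/risk balance acceptable. Section 1.3.4 names myocarditis as a possible complication of the challenge virus, with laboratory changes suggestive of myocardial inflammation in 2 of more than 500 people inoculated. A second, looser entry rule also makes it unclear whether such an enrolment is a protocol deviation.

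**Working it through.** No sample size, power or error rate is involved, so there is no plan figure to reproduce. The check sets the passages side by side and puts example results through each.

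**Step 1: do the two ECG passages concern the same tracing?** Criterion 4 refers to the ECG within 56 days of vaccination. Section 9.2.6.3 schedules an ECG within 56 days of vaccination and another on Day -1 or -2. By the second, the volunteer is already enrolled and vaccinated, so its sentence on enrolment must concern the screening ECG.

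**Step 2: do the limits in criterion 4 bind?** Yes. The note treats abnormal values as able to exclude and ties inclusion after retest to a normal value. Section 4 makes the criterion mandatory.

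**Step 3: example ECGs.** The values are illustrative.

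| Screening ECG | Section 4.1, criterion 4 | Section 9.2.6.3 |
|---|---|---|
| QTcF 455 ms on test and retest, judged not clinically significant | Excluded (455 > 450) | Can be enrolled |
| PR 215 ms on test and retest, judged not clinically significant | Excluded (215 > 210) | Can be enrolled |
| Heart rate 48 bpm on test and retest, judged not clinically significant | Excluded (48 < 50) | Can be enrolled |
| QTcF 455 ms, normal at retest | May be included | No conflict |
| Outside a limit and judged clinically significant | Excluded | Not permitted; no conflict |

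The conflict is confined to ECGs that stay outside a listed limit and are judged not clinically significant.

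**Step 4: laboratory repeats.** The criterion 6 note is triggered by a clinically significant result. Section 9.1.3 is triggered by one that is not clinically significant and may be a testing error.

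- A result judged clinically significant, then normal on repeat: the criterion 6 note provides the repeat; the Section 9.1.3 condition is not met.
- A result above Grade 1, judged not clinically significant and possibly an error, then normal on repeat: Section 9.1.3 provides the repeat; the criterion 6 note does not mention this case.
- A Grade 1 result judged not clinically significant: may be enrolled without a repeat under criterion 6, Section 9.1.3 and Section 9.2.6.2 alike.

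The enrolment limit itself is consistent. What differs is who is said to be entitled to a repeat.

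**The case against.** The best defence is that Section 9.2.6.3 is an assessment section and should be read subject to Section 4. Section 9.1.3 admits only people who comply with the Section 4 criteria and has ECG data reviewed against those criteria. The note closing Section 4.2 repeats that all enrolment criteria must be met. Section 4 tells the investigator to resolve doubts with the sponsor first. On this view, Section 9.2.6.3 covers only ECG findings that breach none of the five limits. That reading has some content: the ECG table in SAP Section 7.4 labels heart rates of 50-54 bpm abnormally low, although they lie inside the criterion 4 range.

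This shows how the conflict could be resolved, but the text does not resolve it. Section 9.2.6.3 speaks of abnormal ECG results without qualification, and the criterion 4 note uses the same adjective for values that may exclude. General statements about compliance do not cancel an explicit permission, and an investigator relying on that permission may see no question to raise with the sponsor.

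The defence does stand on harm. The permission has a second condition, suitability for the population. Exclusion criterion 20 removes people with past arrhythmia or Torsade de Pointes risk factors. ECG and cardiac enzymes are checked again on admission, and Section 4.3 bars challenge for clinically significant ECG abnormalities, though without numeric limits. The 2 myocardial findings resolved without treatment and without ECG changes. A reader might infer that the ECG screen can be bypassed at will; these safeguards do not support that.

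A reader might also infer that the two laboratory rules are mutually exclusive, so that any repeat breaches one of them. That does not follow. Neither passage restricts repeats to its own case. Each grants permission for one situation, and the two can be read together.

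**Conclusion.** The ECG inconsistency is real and should be corrected. A volunteer persistently outside a limit in criterion 4, but judged not clinically significant and suitable for the population, is excluded under Section 4.1 and can be enrolled under Section 9.2.6.3. This rests only on the current wording of the two sections.

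Its size cannot be given. The documents report neither how often such ECGs occur nor how many people will be screened. A reader might be tempted to apply an assumed rate to the 70 in Section 3.1, but that is the ceiling on subjects vaccinated, who have already passed screening.

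The laboratory point is secondary: different repeat-test triggers that need aligning, with a consistent Grade 1 enrolment limit. It affects eligibility only through the result of a repeat.

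Power and the primary analysis are unaffected. The efficacy population comprises all randomized, vaccinated and challenged subjects, whichever rule admitted them.

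**What to change.** Reconcile criterion 4 and Section 9.2.6.3 so that one ECG eligibility rule applies in both places. If the fixed limits are meant to govern, the enrolment sentence in Section 9.2.6.3 can become a cross-reference to criterion 4. If discretion is meant to apply, criterion 4 should say to which findings. Which rule stands is for the sponsor's clinicians.

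In the same amendment, state one condition for a repeat screening laboratory test and use it in both the criterion 6 note and Section 9.1.3.

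The cost is two or three sentences, and possibly slightly more screen failures, depending on the rule chosen. No analysis changes.
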